## **CASE REPORT FORM COMPLETION**

Case report forms are prepared and provided by the sponsor for each participant in electronic format. All data relating to the study must be recorded in CRF. All CRF entries, corrections, and alterations must be made by the investigator or authorized study-site personnel. The investigator must verify that all data entries in the CRF are accurate and correct.

The study data will be transcribed by study-site personnel from the source documents onto an electronic CRF, if applicable. Study-specific data will be transmitted in a secure manner to the sponsor.

Worksheets may be used for the capture of some data to facilitate completion of the CRF. Any such worksheets will become part of the participant's source documents. Data must be entered into CRF in English. The CRF must be completed as soon as possible after a participant visit and the forms should be available for review at the next scheduled monitoring visit.

All participative measurements (eg, pain scale information or other questionnaires) will be completed by the same individual who made the initial baseline determinations whenever possible.

If necessary, queries will be generated in the electronic data capture (eDC) tool. If corrections to a CRF are needed after the initial entry into the CRF, this can be done in either of the following ways:

- Investigator and study-site personnel can make corrections in the eDC tool at their own initiative or as a response to an auto query (generated by the eDC tool).
- Sponsor or sponsor delegate can generate a query for resolution by the investigator and study-site personnel.

## SOURCE DOCUMENTS

At a minimum, source documents consistent in the type and level of detail with that commonly recorded at the study site as a basis for standard medical care must be available for the following: participant identification, eligibility, and study identification; study discussion and date of signed informed consent; dates of visits; dates of blood collection, date and time of start and end of leukapheresis, results of safety and efficacy parameters as required by the protocol; record of all adverse events and follow-up of adverse events; concomitant medication; intervention receipt/dispensing/return records; study intervention administration information; and date of study completion and reason for early discontinuation of investigational intervention or withdrawal from the study, if applicable.

The author of an entry in the source documents should be identifiable.

Specific details required as source data for the study and source data collection methods will be reviewed with the investigator before the study and will be described in the monitoring guidelines (or other equivalent document).

The following data will be recorded directly into the CRF and will be considered source data:

- Race
- Blood pressure and pulse/heart rate
- Height and weight
- Details of physical examination

The minimum source documentation requirements for Section 5.1 and Section 5.2 that specify a need for documented medical history are as follows:

- Referral letter from treating physician or
- Complete history of medical notes at the site
- Discharge summaries

Inclusion and exclusion criteria not requiring documented medical history must be verified at a minimum by participant interview or other protocol required assessment (eg, physical examination, laboratory assessment) and documented in the source documents.

An eSource system may be utilized, which contains data traditionally maintained in a hospital or clinic record to document medical care (eg, electronic source documents) as well as the clinical study-specific data fields as determined by the protocol. This data is electronically extracted for

use by the sponsor. If eSource is utilized, references made to the CRF in the protocol include the eSource system but information collected through eSource may not be limited to that found in the CRF.

## **MONITORING**

The sponsor will use a combination of monitoring techniques (central, remote, or on-site monitoring) to monitor this study.

The sponsor will perform on-site monitoring visits as frequently as necessary. The monitor will record dates of the visits in a study site visit log that will be kept at the study site. The first post-initiation visit will be made as soon as possible after enrollment has begun. At these visits, the monitor will compare the data entered into the CRF with the source documents (eg, hospital/clinic/physician's office medical records); a sample may be reviewed. The nature and location of all source documents will be identified to ensure that all sources of original data required to complete the CRF are known to the sponsor and study-site personnel and are accessible for verification by the sponsor study-site contact. If electronic records are maintained at the study site, the method of verification must be discussed with the study-site personnel.

Direct access to source documents (medical records) must be allowed for the purpose of verifying that the recorded data are consistent with the original source data. Findings from this review will be discussed with the study-site personnel. The sponsor expects that, during monitoring visits, the relevant study-site personnel will be available, the source documents will be accessible, and a suitable environment will be provided for review of study-related documents. The monitor will meet with the investigator on a regular basis during the study to provide feedback on the study conduct.

In addition to on-site monitoring visits, remote contacts can occur. It is expected that during these remote contacts, study-site personnel will be available to provide an update on the progress of the study at the site.

Central monitoring will take place for data identified by the sponsor as requiring central review.

## **ON-SITE AUDITS**

Representatives of the sponsor's clinical quality assurance department may visit the study site at any time during or after completion of the study to conduct an audit of the study in compliance with regulatory guidelines and company policy. These audits will require access to all study records, including source documents, for inspection. Participant privacy must, however, be respected. The investigator and study-site personnel are responsible for being present and available for consultation during routinely scheduled study-site audit visits conducted by the sponsor or its designees.

Similar auditing procedures may also be conducted by agents of any regulatory body, either as part of a national GCP compliance program or to review the results of this study in support of a

regulatory submission. The investigator should immediately notify the sponsor if he or she has been contacted by a regulatory agency concerning an upcoming inspection.

## **RECORD RETENTION**

In compliance with the ICH/GCP guidelines, the investigator/institution will maintain all CRF and all source documents that support the data collected from each participant, as well as all study documents as specified in ICH/GCP Section 8, Essential Documents for the Conduct of a Clinical Trial, and all study documents as specified by the applicable regulatory requirement(s). The investigator/institution will take measures to prevent accidental or premature destruction of these documents.

Essential documents must be retained until at least 2 years after the last approval of a marketing application in an ICH region and until there are no pending or contemplated marketing applications in an ICH region or until at least 2 years have elapsed since the formal discontinuation of clinical development of the investigational product. These documents will be retained for a longer period if required by the applicable regulatory requirements or by an agreement with the sponsor. It is the responsibility of the sponsor to inform the investigator/institution as to when these documents no longer need to be retained.

If the responsible investigator retires, relocates, or for other reasons withdraws from the responsibility of keeping the study records, custody must be transferred to a person who will accept the responsibility. The sponsor must be notified in writing of the name and address of the new custodian. Under no circumstance shall the investigator relocate or dispose of any study documents before having obtained written approval from the sponsor.

If it becomes necessary for the sponsor or the appropriate regulatory authority to review any documentation relating to this study, the investigator/institution must permit access to such reports.

## **STUDY AND SITE START AND CLOSURE**

### **First Act of Recruitment**

The first site open is considered the first act of recruitment and it becomes the study start date.

### **Study Termination**

The sponsor reserves the right to close the study site or terminate the study at any time for any reason at the sole discretion of the sponsor. Study sites will be closed upon study completion. A study site is considered closed when all required documents and study supplies have been collected and a study-site closure visit has been performed.

The investigator may initiate study-site closure at any time, provided there is reasonable cause and sufficient notice is given in advance of the intended termination.

Reasons for the early closure of a study site by the sponsor or investigator may include but are not limited to:

- Failure of the investigator to comply with the protocol, the requirements of the IEC/IRB or local health authorities, the sponsor's procedures, or GCP guidelines
- Inadequate recruitment of participants by the investigator
- Discontinuation of further study intervention development

## **10.4. Appendix 4: Adverse Events: Definitions and Procedures for Recording, Evaluating, Follow-up, and Reporting**

### **ADVERSE EVENT DEFINITIONS AND CLASSIFICATIONS**

#### **Adverse Event**

An AE is any untoward medical occurrence in a clinical study participant administered a medicinal (investigational or non-investigational) product. An AE does not necessarily have a causal relationship with the intervention. An AE can therefore be any unfavorable and unintended sign (including an abnormal finding), symptom, or disease temporally associated with the use of a medicinal (investigational or non-investigational) product, whether or not related to that medicinal (investigational or non-investigational) product. (Definition per ICH)

This includes any occurrence that is new in onset or aggravated in severity or frequency from the baseline condition, or abnormal results of diagnostic procedures, including laboratory test abnormalities.

Note: The sponsor collects adverse events starting with the signing of the ICF (refer to All Adverse Events under Section 8.5.1 for time of last AE recording).

#### **Serious Adverse Event**

A SAE based on ICH and EU Guidelines on Pharmacovigilance for Medicinal Products for Human Use is any untoward medical occurrence that at any dose:

- Results in death
- Is life-threatening  
(The participant was at risk of death at the time of the event. It does not refer to an event that hypothetically might have caused death if it were more severe.)
- Requires inpatient hospitalization or prolongation of existing hospitalization
- Results in persistent or significant disability/incapacity
- Is a congenital anomaly/birth defect
- Is a suspected transmission of any infectious agent via a medicinal product
- Is Medically Important\*

\*Medical and scientific judgment should be exercised in deciding whether expedited reporting is also appropriate in other situations, such as important medical events that may not be immediately life threatening or result in death or hospitalization but may jeopardize the participant or may require intervention to prevent one of the other outcomes listed in the definition above. These should usually be considered serious.

If a serious and unexpected adverse event occurs for which there is evidence suggesting a causal relationship between the study intervention and the event (eg, death from anaphylaxis), the event must be reported as a serious and unexpected suspected adverse reaction even if it is a component of the study endpoint (eg, all-cause mortality).

## **Unlisted (Unexpected) Adverse Event/Reference Safety Information**

An adverse event is considered unlisted if the nature or severity is not consistent with the applicable product reference safety information. For JNJ-3989 and JNJ-6379, the expectedness of an adverse event will be determined by whether or not it is listed in the IB. For ETV, tenofovir disoproxil, and TAF with a marketing authorization, the expectedness of an adverse event will be determined by whether or not it is listed in the package insert.

## **ATTRIBUTION DEFINITIONS**

### **Assessment of Causality**

The causal relationship to study intervention is determined by the Investigator. The following selection should be used to assess all AEs.

#### **Related**

There is a reasonable causal relationship between study intervention administration and the AE.

#### **Not Related**

There is not a reasonable causal relationship between study intervention administration and the AE.

The term "reasonable causal relationship" means there is evidence to support a causal relationship.

## **SEVERITY CRITERIA**

An assessment of severity grade will be made by the investigator using the general categorical descriptors outlined in the DAIDS Toxicity Grading Scale (see Section 10.9, Appendix 9, DAIDS Table).

## **SPECIAL REPORTING SITUATIONS**

Safety events of interest on a sponsor study intervention in an interventional study that may require expedited reporting or safety evaluation include, but are not limited to:

- Overdose of a sponsor study intervention
- Suspected abuse/misuse of a sponsor study intervention
- Accidental or occupational exposure to a sponsor study intervention
- Medication error, intercepted medication error, or potential medication error involving a sponsor medicinal product (with or without patient exposure to the sponsor medicinal product, eg, product name confusion, product label confusion, intercepted prescribing or dispensing errors)
- Exposure to a sponsor study intervention from breastfeeding

Special reporting situations should be recorded in the CRF. Any special reporting situation that meets the criteria of a SAE should be recorded on the SAE page of the CRF.

## PROCEDURES

### All Adverse Events

All adverse events, regardless of seriousness, severity, or presumed relationship to study intervention, must be recorded using medical terminology in the source document and the CRF. Whenever possible, diagnoses should be given when signs and symptoms are due to a common etiology (eg, cough, runny nose, sneezing, sore throat, and head congestion should be reported as "upper respiratory infection"). Investigators must record in the CRF their opinion concerning the relationship of the adverse event to study therapy. All measures required for adverse event management must be recorded in the source document and reported according to sponsor instructions.

In the context of this study, AEs and SAEs associated with/triggered by the liver biopsies, leukapheresis, or blood collection procedures are to be reported to the sponsor.

For all studies with an outpatient phase, including open-label studies, the participant must be provided with a "wallet (study) card" and instructed to carry this card with them for the duration of the study indicating the following:

- Study number
- Statement, in the local language(s), that the participant is participating in a clinical study
- Investigator's name and 24-hour contact telephone number
- Local sponsor's name and 24-hour contact telephone number (for medical personnel only)
- Site number
- Participant number
- Any other information that is required to do an emergency breaking of the blind

### Serious Adverse Events

All SAEs that have not resolved by the end of the study, or that have not resolved upon discontinuation of the participant's participation in the study, must be followed until any of the following occurs:

- The event resolves
- The event stabilizes
- The event returns to baseline, if a baseline value/status is available
- The event can be attributed to agents other than the study intervention or to factors unrelated to study conduct
- It becomes unlikely that any additional information can be obtained (participant or health care practitioner refusal to provide additional information, lost to follow-up after demonstration of due diligence with follow-up efforts)

Suspected transmission of an infectious agent by a medicinal product will be reported as a SAE. Any event requiring hospitalization (or prolongation of hospitalization) that occurs during the course of a participant's participation in a study must be reported as a SAE, except hospitalizations for the following:

- Hospitalizations not intended to treat an acute illness or adverse event (eg, social reasons such as pending placement in long-term care facility)
- Surgery or procedure planned before entry into the study (must be documented in the CRF). Note: Hospitalizations that were planned before the signing of the ICF, and where the underlying condition for which the hospitalization was planned has not worsened, will not be considered SAEs. Any adverse event that results in a prolongation of the originally planned hospitalization is to be reported as a new SAE.

The cause of death of a participant in a study, whether or not the event is expected or associated with the study intervention, is considered an SAE.

## **CONTACTING SPONSOR REGARDING SAFETY**

The names (and corresponding telephone numbers) of the individuals who should be contacted regarding safety issues or questions regarding the study are listed in the Contact Information page(s), which will be provided as a separate document.

## **PRODUCT QUALITY COMPLAINT HANDLING**

A product quality complaint (PQC) is defined as any suspicion of a product defect related to manufacturing, labeling, or packaging, ie, any dissatisfaction relative to the identity, quality, durability, or reliability of a product, including its labeling or package integrity. A PQC may have an impact on the safety and efficacy of the product. Timely, accurate, and complete reporting and analysis of PQC information from studies are crucial for the protection of participants, investigators, and the sponsor, and are mandated by regulatory agencies worldwide. The sponsor has established procedures in conformity with regulatory requirements worldwide to ensure appropriate reporting of PQC information; all studies conducted by the sponsor or its affiliates will be conducted in accordance with those procedures.

### **Procedures**

All initial PQCs must be reported to the sponsor by the study-site personnel within 24 hours after being made aware of the event.

If the defect is combined with a SAE, the study-site personnel must report the PQC to the sponsor according to the SAE reporting timelines (refer to Section 8.5.1). A sample of the suspected product should be maintained for further investigation if requested by the sponsor.

### **Contacting Sponsor Regarding Product Quality**

The names (and corresponding telephone numbers) of the individuals who should be contacted regarding product quality issues are listed in the Contact Information page(s), which will be provided as a separate document.

## 10.5. Appendix 5: Rash Management

Table 6: Management of Rash Events by Severity Grade

	Definition	Study Intervention Action	Activities by Daya	Referral to Dermatologist and Dermatology Activities
Grade 1 rash (with or without pruritus)b	Erythema	Study intervention intake may be continued at the investigator's discretion	
Day 0: optional on site visit for initial rash evaluation may be performed at the investigator's discretion.
 
Safety laboratory assessments may be performed at the investigator's discretion (recommended if visit occurs).
 
Digital pictures* of skin lesions may be taken at the investigator's discretion.
 
Determine if participant was adhering to the recommended sun-protective measures. If appropriate, provide sun protection counseling.
 
Day 1 and thereafter: appropriate follow-up visits at the investigator's discretion until resolution of rash.
 
Safety laboratory assessments and photography (digital pictures* of skin lesions) may be performed at the investigator's discretion.
 
* Digital pictures to be taken at the clinical site upon consent of the participant.
	Not required
Grade 2 rash (with or without pruritus)b	Diffuse, maculopapular rash, or dry desquamation	Study intervention intake may be continued at the investigator's discretion	
Day 0: required on-site visit (if a visit is not possible, telephone contact with the participant should take place to collect information and give advice on the necessary measures to be taken).
 
Safety laboratory assessments may be performed at the investigator's discretion (recommended).
 
Digital pictures* of skin lesions may be taken at the investigator's discretion. Digital pictures* of skin lesions are recommended in case consultation of a dermatologist is required. Determine if participant was adhering to the recommended sun-protective measures. If appropriate, provide sun protection counseling.
 
Day 1 and thereafter: appropriate follow-up visits at the investigator's discretion until resolution of rash or until clinical stability is reached.
	
Referral to dermatologist at the discretion of the investigatorc
 
Biopsy not required, but may be performed at the dermatologist's discretion

**Table 6: Management of Rash Events by Severity Grade**

Definition	Study Intervention Action	Activities by Daya	Referral to Dermatologist and Dermatology Activities
Grade 3 rashb	
Vesiculation, moist desquamation, or ulceration OR
 
Any cutaneous event with 1 of the following:
 
 
- Elevations in AST/ALT <math>>2\times</math>baseline value
 
- Fever <math>>38^{\circ}\text{C}</math> or <math>100^{\circ}\text{F}</math>
 
- Eosinophils <math>>1.00\times 10^3/\mu\text{L}</math>
 
- Serum sickness-like reaction
 
	
Must permanently discontinue JNJ-3989; no rechallenge allowed
 
NA treatment may be discontinued based on investigator judgement in consultation with the sponsor
 
Day 0: required on-site visit.
 
Safety laboratory assessments required to be performed.
 
Digital pictures* of skin lesions may be taken at the investigator's discretion (recommended).
 
Determine if participant was adhering to the recommended sun-protective measures. If appropriate, provide sun protection counseling.
 
Day 1: required on-site visit.
 
Safety laboratory assessments required to be performed.
 
Digital pictures* of skin lesions may be taken at the investigator's discretion (recommended).
 
Further visit(s): appropriate follow-up required until resolution of rash or until clinical stability is reached.
 
Safety laboratory assessments and photography (digital pictures* of skin lesions) are recommended to be performed until the rash severity resolves to grade 2 or grade 1.
 
* Digital pictures to be taken at the clinical site upon consent of the participant.
	
Requiredc
 
Biopsy not required, but may be performed at the dermatologist's discretion.

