## 7. DISCONTINUATION OF INVESTIGATIONAL INTERVENTION AND PARTICIPANT DISCONTINUATION/WITHDRAWAL

### 7.1. Discontinuation of Study Intervention

With the implementation of Protocol Amendment 5, all participants had to stop JNJ-6379 treatment immediately.

Treatment with JNJ-3989 and/or PegIFN- $\alpha$ 2a must be discontinued if any of the criteria listed below apply. If JNJ-3989 is discontinued, PegIFN- $\alpha$ 2a should also be discontinued. If PegIFN- $\alpha$ 2a is discontinued, JNJ-3989 should be continued. NA treatment may be continued or, in consultation with the sponsor or discontinued based on investigator judgement.

- The participant withdraws consent to receive study intervention.
- The investigator believes that for safety reasons or tolerability reasons (eg, AE) it is in the best interest of the participant to discontinue JNJ-3989 (and, if applicable, PegIFN- $\alpha$ 2a).
- The participant becomes pregnant.
- The participant has a  $\geq$ grade 3 rash (see Section 10.5, Appendix 5, Rash Management) or allergic reaction (see Section 8.5.7.2).
- The participant has signs of hepatic decompensation (ie, clinical evidence of ascites, bleeding varices, or hepatic encephalopathy) or an increase in direct bilirubin  $>1.5$ x ULN in combination with INR  $\geq 1.5$ x ULN or albumin  $<3.0$  g/dL.
- The participant has a confirmed  $\geq$ grade 3 eGFRcr abnormality and a drop from baseline of  $>10$  mL/min/1.73 m^2, considered at least possibly related to JNJ-3989 (or PegIFN- $\alpha$ 2a) that persists despite changing tenofovir disoproxil to ETV or TAF (if the patient was receiving tenofovir disoproxil) (see Section 8.5.6.4).
- The participant has a confirmed QTcF prolongation (defined as a QTcF value of  $>500$  ms, or an increase from baseline of  $>60$  ms) at any given time point.
- The participant requires  $\geq 7$  days of treatment with any of the disallowed medications listed in Section 6.5 and does not intend to discontinue treatment with the disallowed medication.

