**Table 6: Management of Rash Events by Severity Grade**

	Definition	Study Intervention Action	Activities by Daya	Referral to Dermatologist and Dermatology Activities
Grade 4 rash	Exfoliative dermatitis OR  Mucous membrane involvement in at least 2 distinct sites OR  Erythema multiforme major OR  Stevens-Johnson syndrome OR  Toxic epidermal necrolysis OR  Necrosis requiring surgery	Must permanently discontinue JNJ-3989; no rechallenge allowed  NA treatment may be discontinued based on investigator judgement in consultation with the sponsor	Day 0 : required on-site visit.  Safety laboratory assessments required to be performed.  Digital pictures* of skin lesions may be taken at the investigator's discretion (recommended).  Determine if participant was adhering to the recommended sun-protective measures. If appropriate, provide sun protection counseling.  Day 1 : required on-site visit.  Safety laboratory assessments required to be performed.  Digital pictures* of skin lesions may be taken at the investigator's discretion (recommended).  Further visit(s) : appropriate follow-up required until resolution of rash or until clinical stability is reached.  Safety laboratory assessments and photography (digital pictures* of skin lesions) are recommended to be performed until the rash severity resolves to grade 2 or grade 1.	Required c  Biopsy required and to be performed as soon as possible after the onset of the rash.

AE: adverse event; ALT: alanine aminotransferase; AST: aspartate aminotransferase; NA: nucleos(t)ide analog.

a Day 0 of the rash is the first day of investigator assessment and not the first day of rash as reported by the participant. The initial visit should be conducted as soon as possible after the participant contacts the investigator to report the AE (ie, preferably on Day 0). The initial visit and subsequent visits to manage the rash may require unscheduled visit(s).

[figure not shown]
b The participant should be advised to contact the investigator immediately if there is any worsening of the rash, if any systemic signs or symptoms appear, or if mucosal involvement develops. In case the rash evolves to a higher grade than that first observed, management of the rash should follow the guidelines indicated for the higher grade.

c If applicable, dermatologist visit should occur preferably within 24 hours after onset of rash.

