Visual Changes (assessed from baseline)	Visual changes causing no or minimal interference with usual social & functional activities	Visual changes causing greater than minimal interference with usual social & functional activities	Visual changes causing inability to perform usual social & functional activities	Disabling visual loss in affected eye(s)

dB: decibel; kHz: kilohertz; NAP: not applicable

PARAMETER	SYSTEMIC			
	GRADE 1 MILD	GRADE 2 MODERATE	GRADE 3 SEVERE	GRADE 4 POTENTIALLY LIFE- THREATENING
Acute Allergic Reaction	Localized urticaria (wheals) with no medical intervention indicated	Localized urticaria with intervention indicated OR Mild angioedema with no intervention indicated	Generalized urticaria OR Angioedema with intervention indicated OR Symptoms of mild bronchospasm	Acute anaphylaxis OR Life threatening bronchospasm OR Laryngeal edema
Chills	Symptoms causing no or minimal interference with usual social & functional activities	Symptoms causing greater than minimal interference with usual social & functional activities	Symptoms causing inability to perform usual social & functional activities	NAP
Cytokine Release Syndromeb	Mild signs and symptoms AND Therapy (ie, antibody infusion) interruption not indicated	Therapy (ie, antibody infusion) interruption indicated AND Responds promptly to symptomatic treatment OR Prophylactic medications indicated for $\leq 24$ hours	Prolonged severe signs and symptoms OR Recurrence of symptoms following initial improvement	Life threatening consequences (eg, requiring pressor or ventilator support)
Fatigue or Malaise Report only 1	Symptoms causing no or minimal interference with usual social & functional activities	Symptoms causing greater than minimal interference with usual social & functional activities	Symptoms causing inability to perform usual social & functional activities	Incapacitating symptoms of fatigue or malaise causing inability to perform basic self care functions
Fever (non axillary temperatures only)	38.0°C to $<38.6^{\circ}\text{C}$ or 100.4°F to $<101.5^{\circ}\text{F}$	$\geq 38.6^{\circ}\text{C}$ to $<39.3^{\circ}\text{C}$ or $\geq 101.5^{\circ}\text{F}$ to $<102.7^{\circ}\text{F}$	$\geq 39.3^{\circ}\text{C}$ to $<40.0^{\circ}\text{C}$ or $\geq 102.7^{\circ}\text{F}$ to $<104.0^{\circ}\text{F}$	$\geq 40.0^{\circ}\text{C}$ or $\geq 104.0^{\circ}\text{F}$

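### The fever limit for a grade 3 rash in Table 6 is printed as two different temperatures (38°C and 100°F), and it decides a permanent stop of JNJ-3989

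*Protocol*

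**What the plan says.** Protocol Section 10.5 (Appendix 5), Table 6, defines grade 3 rash in two ways. The first is by appearance: vesiculation, moist desquamation or ulceration. The second is "Any cutaneous event with 1 of the following", followed by a list of AST/ALT elevation above twice baseline, fever, raised eosinophils, and a serum sickness-like reaction. The fever item reads "Fever >38^{\circ}\text{C} or 100^{\circ}\text{F".

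The action for grade 3 is "Must permanently discontinue JNJ-3989; no rechallenge allowed". Section 7.1 repeats the stop by listing a rash of at least "grade 3 rash (see Section 10.5, Appendix 5, Rash Management) or allergic reaction" among the mandatory discontinuation criteria. It adds that PegIFN-α2a should stop when JNJ-3989 stops. For grade 1 and grade 2 rash, Table 6 says instead: "Study intervention intake may be continued at the investigator's discretion". Footnote b to the table covers a rash that worsens: "management of the rash should follow the guidelines indicated for the higher grade".

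The protocol gives paired fever temperatures in one other place, the fever row of the DAIDS table in Section 10.9 (Appendix 9). There, grade 1 fever starts at 38.0°C, paired with 100.4°F.

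**The concern.** A limit given in two units should be the same temperature in both, and these two are not. If the figures are meant as equivalents, one of them is wrong. If the word joining them is taken literally, so that exceeding either is enough, the lower figure always governs, the 38°C figure has no effect, and the rule is triggered below the temperature at which the protocol's own fever scale begins. The text does not say which is intended.

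The figure matters because it separates a discretionary decision from an irreversible one. Two sites applying the same table, one reading its thermometer in Celsius and the other in Fahrenheit, could manage the same participant differently: one must stop JNJ-3989 for good, the other may continue. Because of footnote b, the limit is applied throughout a rash episode as well as at first assessment. Grade 3 also makes on-site visits with safety laboratory tests on Day 0 and Day 1 compulsory, together with referral to a dermatologist.

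**Working it through.** **Inputs.** Table 6 fever limit: 38°C and 100°F. Appendix 9 fever row boundaries: 38.0/100.4, 38.6/101.5, 39.3/102.7 and 40.0/104.0 (°C/°F). Formulas: F = C × 9/5 + 32 and C = (F − 32) × 5/9.

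**Step 1: convert the Table 6 pair.**
- 38 × 9/5 + 32 = 100.4°F, against 100°F printed: a difference of 0.4°F.
- (100 − 32) × 5/9 = 37.78°C, against 38°C printed: a difference of 0.22°C.

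The printed pair does not reproduce.

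**Step 2: see how closely the protocol converts elsewhere.**

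| Source | Printed °C | Converted °F | Printed °F | Printed minus converted |
|---|---|---|---|---|
| Appendix 9 | 38.0 | 100.40 | 100.4 | 0.00 |
| Appendix 9 | 38.6 | 101.48 | 101.5 | +0.02 |
| Appendix 9 | 39.3 | 102.74 | 102.7 | −0.04 |
| Appendix 9 | 40.0 | 104.00 | 104.0 | 0.00 |
| Table 6 | 38 | 100.40 | 100 | −0.40 |

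The Appendix 9 pairs agree to within 0.04°F. The Table 6 pair is out by ten times that (0.40/0.04).

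**Step 3: find the readings on which the two figures disagree.** The "greater than" sign is taken to apply to both figures, and the thermometer to read in steps of 0.1.

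| Reading °C | Same in °F | Above 38°C? | Above 100°F? |
|---|---|---|---|
| 37.7 | 99.86 | No | No |
| 37.8 | 100.04 | No | Yes |
| 37.9 | 100.22 | No | Yes |
| 38.0 | 100.40 | No | Yes |
| 38.1 | 100.58 | Yes | Yes |

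Three Celsius readings are affected (37.8, 37.9 and 38.0). On a Fahrenheit thermometer the affected readings are 100.1, 100.2, 100.3 and 100.4.

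**Step 4: narrow to the participants for whom it matters.** An event with any other grade 3 sign, or a grade 4 feature, already forces the stop whatever the temperature. The discrepancy therefore changes the action only for a rash that is otherwise grade 1 or 2, with a temperature in the band from Step 3.

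**The case against.** The case for treating this as editorial has five parts.

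- **Working unit.** SAP Section 5.6.3.2 analyses body temperature in °C, and both Table 6 figures are whole degrees, so 100 may simply be 100.4 rounded for convenience. That is a plausible origin. But the SAP section concerns the analysis of vital signs, and neither document says which unit sites use to manage a rash.
- **Literal reading.** If either limit suffices, the rule is determinate and errs towards caution: a participant may be stopped slightly early, but nobody is dosed through a grade 3 rash. This is correct as far as it goes. It leaves one printed figure with no function, and an unnecessary stop cannot be reversed.
- **Comparison with Appendix 9.** The DAIDS fever row applies to non-axillary temperatures, Table 6 names no route, and a sign accompanying a rash need not share the threshold for a fever adverse event. This is fair. Appendix 9 does not set the rash limit; it shows only how this protocol pairs the two units at 38.0°C.
- **Small practical effect.** The band is narrow, and the study targets 24 participants in Panels 1 and 2, plus 4 in Panel 3. Within the band the investigator can still stop treatment for safety, and participants are told to report systemic signs at once. All of this stands and limits the weight of the point.
- **Timing.** SAP Amendment 2 is dated 09 February 2024, so dosing may be over and a note to sites of little use. This is an inference, since the documents supplied do not say so.

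These arguments reduce the importance of the point. None of them makes the two figures agree.

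**Conclusion.** The concern holds: the threshold is wrong as written. Its two figures differ by 0.22°C (0.4°F), and for readings of 37.8 to 38.0°C in an otherwise grade 1 or 2 rash they lead to different actions, one of which is permanent. This is a minor safety-threshold correction that should be made. It does not bear on the Week 40 endpoint, the analysis sets or the sample size.

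The conclusion rests on three assumptions. The first is that the protocol prints 100 and not 100.4 in Table 6. The text supplied shows a clean 100 and preserves 100.4 in Appendix 9, but a decimal lost in conversion cannot be wholly excluded and is easily checked against the signed document. The second is that the inequality applies to both figures; if 100°F itself counts, a reading of 100.0°F joins the band. The third is a thermometer resolution of 0.1 degree. The documents give no rate for a rash with a temperature in this range, so no number of affected participants is estimated.

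**What to change.** Replace the fever item in the grade 3 row of Table 6 with a single limit in matching units. The natural choice is above 38.0°C (above 100.4°F), which follows the pairing in the Appendix 9 fever row. If the clinical team wants the lower limit, write above 37.8°C (above 100°F). The choice is a clinical one and should be stated in the amendment. Tell sites which figure applies if any participant can still receive JNJ-3989. The cost is one line of protocol text and a short notice; no data collection or analysis changes.
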